#### **9.2.5 Long-Term Sequelae of Virus Injection**

PVSRIPO does not encode foreign genetic material, polioviruses are unable to insert viral genetic material in the host genome and polioviruses are incapable of inducing latent or chronic CNS infection. Therefore, PVSRIPO is unable to induce long-term expression of foreign polypeptides or long-term persistence of virus replication. Thus, there are no long-term neurologic consequences to intracerebral PVSRIPO administration in study subjects. For these reasons, no specific measures to analyze the potential for persistence of virus replication in the CNS of long-term survivors are indicated.

Prolonged gastrointestinal propagation of polioviruses, associated with prolonged virus shedding with stool, has been reported in select individuals with acquired or rare inherited immunodeficiency disorders. Primate toxicology results indicate that extraneuronal dissemination and shedding of PVSRIPO with stool do not occur after intracerebral inoculation. In addition, the use of PVSRIPO in human subjects with recurrent malignant glioma in phase I have not demonstrated this phenomena.

#### **9.2.6 Risks of Phlebotomy**

Drawing blood or inserting an intravenous catheter into an arm vein may result in bruising or swelling in the area of the insertion, bleeding at the site of the needle puncture, light headedness, fainting and very rarely, local infection, which may be severe. These risks are reduced by the fact that the blood will be drawn by a qualified physician, nurse or phlebotomist (a professional trained to draw blood).

#### **9.2.7 Risks to Household Contacts of Study Subjects**

Primate toxicology studies showed that intracerebral infusion of PVSRIPO does not lead to extraneuronal dissemination or replication and, hence, is not associated with virus shedding. In addition, this also has not been observed with the use of PVSRIPO in human subjects with recurrent malignant glioma in phase I trials. Therefore, and because poliovirus transmission occurs via the fecal-oral route, the likelihood of unintended exposure of patient household contacts is exceedingly low. If accidental exposure occurred, it would equal the risk of exposure to any type 1 Sabin vaccine virus or vaccine virus derivatives. Thus, in essence, exposure with PVSRIPO is equal to oral immunization with a safe version of type 1 Sabin. Since type 1 Sabin vaccine virus or vaccine virus derivatives have to be considered part of the human environment, exposure to PVSRIPO would not represent an added risk beyond the possibility for exposure that already exists. Study subjects will be advised of the risks of exposure to unvaccinated household contacts.

### **9.2.8 Unacceptable Toxicities**

Clinical trials using PVSRIPO in breast tumor patients have not been performed. Since the overall risk classification of this research is unknown we plan to take the following approaches to ensure patient safety:

- I. We will stagger enrollment of each patient by at least 4 weeks, which will be sufficient time to implement dose reduction or other safety measures based on adverse events observed.
- II. The study will only treat 6 patients total. However, the trial will be paused for enrollment and undergo reevaluation if two patients have any Grade 3 or any Grade 4 toxicity that is not reversible within 2 weeks after surgery (~24-34 days after PVSRIPO, depending on when the surgery is performed), or any life-threatening event, or treatment-related death will be considered an unacceptable toxicity. Any grade 2 or higher serious autoimmune toxicities particularly those affecting vital organs (e.g. cardiac, renal, CNS) will be considered an unacceptable toxicity. Also, the study will be paused to enrollment if a patient death occurs within a month after PVSRIPO injection possibly or likely related to PVSRIPO.

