#### **5.4 Selection of Subjects**

**Eligibility Criteria:** This pilot study will include women with stage II-IV invasive breast cancer scheduled to undergo surgical resection. Target enrollment is six women with invasive breast cancer over 24 months. Patients will be recruited among patients receiving their treatment for breast cancer at Duke Cancer Institute (DCI). Any subjects who do not have evaluable tumor tissue from both the pre-treatment biopsy and post-treatment surgery will be replaced.

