## 9 INVESTIGATIONAL PLAN

### 9.1 Study Design

This is a single institution pilot study designed to assess PVSRIPO-mediated intratumoral bioactivity, inflammation and immune cell infiltration in 6 patients with invasive breast cancer. To maximize immunological stimulation, we will wait at least 2 weeks (ideal 3-4 weeks) after the last dose of chemotherapy or steroids to administer the polio vaccine booster. PVSRIPO will be injected into the tumor mass at  $1 \times 10^8$  TCID50 7-10 days after polio vaccine booster is administered.

Biopsy material will be obtained from tumor tissue immediately prior to virus administration and resected tumor tissue will be obtained at 10-20 days (ideally 12-16) after PVSRIPO at the time of surgical resection. The PVSRIPO-treated tumor tissue will be transported to Surgical Pathology by the Brain Tumor BioRepository (BTBR) Team, as directed by [name], MD or per clinical protocol, for gross examination and research tissue procurement, thereby safe-guarding the diagnostic integrity of the specimen. Additional expertise in breast pathology will be provided by [name] [name], MD, PhD.

Tissue deemed appropriate for collection (i.e. wasteful excess and of no diagnostic value) will be collected by the Brain Tumor BioRepository (BTBR) Team, as directed by [name], PhD, and transported to her lab for correlative molecular and immune analyses. Our primary objective is to determine change in the amount of tumor infiltrating immune cells in tumor tissue pre- and post-injection of PVSRIPO by H&E. We will also evaluate inflammatory and immune signatures using inflammatory and innate/adaptive arrays, CD155 expression and immune cell infiltrate by IHC and tumor infiltrating immune cells by flow cytometry (post-injection only).

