4. If a study pause occurs due to adverse events observed according to Section 9.2.8 and these adverse events are concluded to be possibly or likely related to PVSRIPO injection and it is deemed safe to continue the study, then we will continue to enroll patients at a lower dose of  $5 \times 10^7$  TCID50, the dose currently being investigated in the phase 2 recurrent malignant glioma study in adults and a phase 1b study in recurrent malignant glioma in pediatric patients.

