## **12 SCREENING AND ON-STUDY TESTS AND PROCEDURES**

Informed consent will occur after confirming tumor size by imaging per SOC between days -28 and -7. After obtaining informed consent and during screening (days -28 to -7), women with invasive breast cancer will undergo complete history and physical exam, blood work including CBC, CMP, and pregnancy test (if applicable). An ultrasound, mammogram, or breast MRI showing a residual breast tumor at least 1 cm in size before PVSRIPO injection is required.

After completing informed consent for the protocol, the patient will receive a polio vaccine booster (day -7). On day 0, an ultrasound guided core biopsy will be performed at radiology prior to injection of PVSRIPO into the tumor. Injection will be performed in Duke Breast Radiology and the patients will be transferred to Duke Cancer Center clinic 2-2. Vital signs will be monitored every 15 minutes for an hour prior to patient discharge. On day 10-20

(ideal 12-16 days), the patient will undergo SOC surgery. Part of the excised tumor will be transported to Surgical Pathology by the Brain Tumor BioRepository (BTBR) Team, as directed by [name], MD or per clinical protocol, for gross examination and research tissue procurement. Additional expertise in breast pathology will be provided by [name] [name], MD, PhD.

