### **12.1 Pre-treatment Period**

Women with stage II-IV invasive breast cancer with a residual tumor mass of at least 1 cm by imaging, after completion of neoadjuvant chemotherapy will be included in this study. A polio vaccine booster will be given 7 to 10 days before PVSRIPO injection. Thirty-five ml whole blood will be drawn for immunological profiling before polio vaccine booster.

 At the discretion of the physician, MMG or ultrasound may be done the day prior to surgery

 MMG or ultrasound only done at the 6 ( $\pm$  1) month follow-up visit.

 At 1 month follow-up visit only.

 This is a take-home kit and does not involve a clinic/hospital visit. Days refer to days after PVSRIPO.

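### The 4-week stagger has no stated anchor and, counted injection to injection, can end before the day that decides whether a Grade 3/4 toxicity counts

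*Combined protocol and SAP*

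**What the plan says.** Section 9.2.8 gives two protections, introduced by the statement that PVSRIPO has not been tried in breast tumor patients and that the overall risk is unknown.

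- Item I sets the spacing: "We will stagger enrollment of each patient by at least 4 weeks, which will be sufficient time to implement dose reduction". The sentence goes on to mention other safety measures prompted by the adverse events seen. It does not say which event in one woman's course starts the 4 weeks or which event in the next woman's course ends them.
- Item II sets the main trigger: "the trial will be paused for enrollment and undergo reevaluation if two patients have any Grade 3 or any Grade 4 toxicity". The toxicity is qualified as "toxicity that is not reversible within 2 weeks after surgery (~24-34 days after PVSRIPO, depending on when the surgery is performed".

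Section 9.3, item 4, says what follows a pause. If the events are judged possibly or likely related to PVSRIPO and it is safe to go on, "then we will continue to enroll patients at a lower dose of" 5 x 10^7 TCID50. Until then the dose is 1 x 10^8 TCID50.

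The timings come from three other places. Section 9.1: "resected tumor tissue will be obtained at 10-20 days (ideally 12-16) after PVSRIPO at the time of surgical resection". Section 5.3 gives day 14 as the nominal surgery day. Section 12.1: "A polio vaccine booster will be given 7 to 10 days before PVSRIPO injection". On accrual, section 5.4 says "Target enrollment is six women with invasive breast cancer over 24 months".

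**The concern.** Item I claims that the spacing leaves time to lower the dose for the next woman. Item II defines the event that leads to the lower dose so that it cannot be established until two weeks after surgery. A 28-day spacing falls inside the 24-to-34-day range in which that date lies. Continuous adverse event recording does not remove the problem, because failure to reverse by a given date cannot be known before that date.

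The woman at risk is the one who follows the second affected patient. If the second persistent Grade 3 or 4 toxicity is in the woman just treated, the rule cannot be met until her deciding date. One more woman may by then have received the full dose that the protocol would have halved. This is the first use of the agent in breast tumors, and the stagger is a stated safeguard.

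**Working it through.** **Inputs.** Stagger: 4 weeks = 28 days (9.2.8, item I). Permitted surgery day d: 10 to 20, ideally 12 to 16 (9.1), nominally 14 (5.3). Reversal limit: surgery + 14 days (9.2.8, item II). Booster: 7 to 10 days before injection (12.1). Consent: at least 7 days before injection (section 12).

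**Step 1: the plan's own figure.** Deciding day = d + 14. For d = 10 this is 24 and for d = 20 it is 34, which reproduces the protocol's range of about 24 to 34.

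**Step 2: injection-to-injection stagger.** The earliest next injection is day 28. Margin = 28 − (d + 14) = 14 − d.

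| Surgery day | Deciding day | Margin (days) |
|---|---|---|
| 10 | 24 | +4 |
| 11 | 25 | +3 |
| 12 | 26 | +2 |
| 13 | 27 | +1 |
| 14 | 28 | 0 |
| 15 | 29 | −1 |
| 16 | 30 | −2 |
| 17 | 31 | −3 |
| 18 | 32 | −4 |
| 19 | 33 | −5 |
| 20 | 34 | −6 |

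The next injection may come before the deciding date for d = 15 to 20. That is 6 of 11 permitted days, by 1 to 6 days. Within the ideal window it is d = 15 and 16, which is 2 of 5 days, by 1 to 2 days. At the nominal day 14 the two dates coincide. These are counts of permitted days, not predicted frequencies.

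**Step 3: other anchors.**

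| 4 weeks counted from → to | Smallest gap between injections | Always past day 34? |
|---|---|---|
| Injection → injection | 28 | No |
| Booster → booster | 28 + 7 − 10 = 25 | No |
| Injection → next woman's booster or consent | 28 + 7 = 35 | Yes, by 1 day |

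Only the last reading clears the latest deciding day in every case, and the text does not state it.

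**Step 4: how many women.** On the injection-to-injection reading, the woman after next cannot be injected before day 2 × 28 = 56, well past 34. So at most one extra woman per trigger is treated too early.

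**Step 5: how often the minimum binds.** 24 months / 6 women = one woman per 4 months on average. The 28-day minimum matters only when two candidates arrive close together.

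**The case against.** The strongest reply is that item I speaks of events observed, not of the date in item II, and that action need not wait. Section 14.1 commits the investigator to suitable action if Grade III or IV events are unexpectedly frequent, and it names dose de-escalation. Section 13.4 lets the research monitor stop the study or remove individual women. Life-threatening events, treatment-related deaths and serious autoimmune toxicities of Grade 2 or higher are unacceptable under 9.2.8 without any wait. All of this stands and narrows the point. None of it requires that the next injection be held, or sets a time. The one dose reduction that the protocol defines still depends on the pause.

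A second reply is that the reversal condition may qualify Grade 4 only. The sentence allows that reading. Grade 3 events would then count at once, and the gap would apply to Grade 4 alone.

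Three stronger readings are tempting, and the documents do not support them.

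- A reader might infer that a stagger on enrollment runs from consent to consent and so permits far closer injections, because "Informed consent will occur after confirming tumor size by imaging per SOC between days -28 and -7". But the inclusion criteria in section 5.4 place consent before enrollment, and they make booster receipt and a positive polio titer conditions of eligibility. Equating enrollment with consent is therefore weakly based, and it would defeat item I's own purpose.
- A reader might infer that a pause to enrollment leaves a woman who is already boosted free to be injected. Section 14.1 says that the study is halted once toxicity stopping rules are met, which largely answers this after the trigger. The gap lies before the trigger.
- A reader might infer that 4 weeks is always too short. It is not: surgery on days 10 to 13 leaves 1 to 4 days in hand, and an injection-to-booster anchor always clears.

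**Conclusion.** The concern holds in a limited form. The stagger has no stated anchor. If it runs from injection to injection, the claim that 4 weeks is enough time to reduce the dose fails for 6 of the 11 permitted surgery days, by 1 to 6 days, and has no margin on the nominal day.

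This rests on three assumptions: the injection-to-injection reading, the reversal condition applying to Grade 3 as well as Grade 4, and nobody choosing to hold the next injection.

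The effect is at most one extra woman at 1 x 10^8 TCID50 per trigger, and only after the second affected patient. The documents give no toxicity rate or arrival pattern from which to put a probability on that, so the day counts should not be read as one. With about one woman per 4 months, the case will be uncommon. The change is still worth making, because a minimum interval exists for exactly the case in which two women come close together.

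**What to change.** Replace item I of section 9.2.8 with:

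*PVSRIPO injections will be at least 4 weeks apart. If the previous woman has a Grade 3 or 4 toxicity that has not resolved, no further woman, including one already enrolled or boosted, will be injected until that toxicity has resolved or rule II has been applied at 2 weeks after her surgery, and any resulting re-evaluation is complete.*

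This fixes the anchor and ties any delay to an open event, so a woman who follows an uneventful case is not held back.

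No visit is added. Adverse events are already recorded continuously (Table 1). The 1-month visit, with its window of ±10 days, covers about day 20 to 40 if a month is taken as 30 days, and so contains every deciding date from day 24 to 34.

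With surgery inside its window, the latest deciding day is 34. If the next injection is given on day 35, the delay is 35 − 28 = 7 days, and it arises only while a Grade 3 or 4 toxicity is unresolved. If rule II is met, the re-evaluation takes further time, but the protocol already requires that. The real cost is that a candidate whose own surgery cannot move could lose her slot.

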4. If a study pause occurs due to adverse events observed according to Section 9.2.8 and these adverse events are concluded to be possibly or likely related to PVSRIPO injection and it is deemed safe to continue the study, then we will continue to enroll patients at a lower dose of  $5 \times 10^7$  TCID50, the dose currently being investigated in the phase 2 recurrent malignant glioma study in adults and a phase 1b study in recurrent malignant glioma in pediatric patients.

#### **9.4 Rationale for Correlative Studies**

As this is a pilot study with exploratory endpoints only, correlative studies will be used to assess PVSRIPO tumor bioactivity. Specifically, the study will investigate PVSRIPO-mediated inflammation and immunity in women with stage II-IV invasive breast cancer. Greater detail is provided in Section 8.

#### **9.5 Early Study Termination**

This study can be terminated at any time for any reason by the PI or Sponsor. If this occurs, all subjects on study will be notified as soon as possible. Additional procedures and/or follow up should occur in accordance with Section 12.6, which describes criteria for Early Withdrawal of Subject(s).

### **10 STUDY DRUG**

#### **10.1 Names, Classification, and Mechanism of Action**

PVSRIPO is the live attenuated poliovirus (PV) serotype 1 (SABIN) vaccine with its internal ribosomal entry site (IRES) element replaced with that of human rhinovirus type 2. IRES exchange causes an inability of PVSRIPO to drive translation of its genome in normal cells (35, 36). Thus, PVSRIPO is devoid of neuropathogenicity after high-dose intracerebral inoculation in non-human primates (13) and in humans. Because PVSRIPO is a version of the serotype 1 live-attenuated (Sabin) poliovirus vaccine (PV1), its immunogenic properties and potential for long-term sequelae are expected to be similar. PV1S has been safely administered to >10 billion individuals worldwide without untoward long-term immunogenic sequelae. The main immunogenic effect of administration of PV1S to human subjects is neutralizing immunity to poliovirus.

#### **10.2 Supply, Receipt, and Storage**

PVSRIPO is formulated in 50 mM sodium phosphate in 0.9% sodium chloride, pH 7.4 with 0.2% human serum albumin. It is provided in sterile, single use containers. PVSRIPO must be stored at less than or equal to -70°C. Once thawed, it is a clear colorless liquid with no evidence of particulates or foreign matter. The PVSRIPO being utilized in this study was manufactured at the Biopharmaceutical Development Program/National Cancer Institute (NCI)-Frederick.

#### **10.3 Dispensing and Preparation**

The study agent and vehicle will be supplied to the Investigational Pharmacy by the Sponsor or their representative. The study agent will be shipped via approved methods in the appropriate packaging on dry ice. Storage of the study agent at -70°C has been empirically determined to not compromise biological and biophysical properties for at least 5 years.

The agent will be stored long-term in an ultra-low temperature freezer (e.g., less than or equal to -80°C freezer).

For aliquot preparation, the agent will be thawed slowly on ice (~4°C) and kept at that temperature. Thawed vials of PVSRIPO are stable at 4°C for 48 hours. The supplier will provide the study agent's potency (as tissue culture infectious doses [TCID]) and will also supply the appropriate vehicle for aliquot preparation. Aliquot preparation will occur in the Investigational Pharmacy. All handling of the study agent will occur in a biosafety cabinet or a similarly contained environment.

The study agent will be in a disposable, hypodermic needle with a safety sheath to cover the needle using a one-handed technique after the agent is drawn into the syringe. The sheathed needle is then removed from the syringe containing the study agent, aliquoted at the desired dose, and the syringe will be capped. The capped syringe will be transported to the site of patient injection in a 'ziplock' bag placed in a portable cooler while maintaining a temperature of 4°C.

Each patient will be injected with a total intratumoral dose of  $1 \times 10^8$  TCID50 PVSRIPO in physiologic saline stabilized with 0.2% human serum albumin. The injection surface will be cleaned with Chloraprep or betadine and allowed to dry. A local anesthetic agent will be applied to the injection area. There will be a single entry point into the breast. The study agent in 0.6 mL will be loaded into a 1 cc syringe connected to the injection needle. Under direct ultrasound visualization, a 20 or 21-gauge needle will be inserted into the tumor. Following visualization of the needle tip within the tumor, study agent will be injected over 10-15 seconds by hand injection. The needle tip will then be repositioned to another site within the tumor and the injection repeated. A total of 3-6 sites will be injected with the total study dose evenly divided among sites. The location of sites will be selected by the performing radiologist with the aim of evenly distributing the study agent over the volume of a typically irregularly shaped tumor. All injections will be performed under direct real-time ultrasound visualization. The needle will then be removed very slowly.

Post-Injection pressure will be applied to the injection site(s) with sterile gauze for at least 30 seconds. The injection site and surrounding area will be swabbed with alcohol. After a change of gloves, the injected lesion(s) will be covered with an absorbent pad and dry occlusive dressing. Exterior of the occlusive dressing will be wiped with alcohol. Following injection and bandaging, the patients will be transferred to clinic 2.2. Vital signs will be monitored every 10 minutes for an hour prior to patient discharge. Patients will be advised to keep the injection site(s) covered. Bandage will be replaced when the patient returns to the clinic 1-2 days after PVSRIPO injection. Patients will be advised to leave the dressing on for 2-3 more days. If the bandage falls off at home, the patients will be asked to replace the bandage. They will receive instructions on how to replace bandage and will be provided with gloves and plastic Ziploc disposal bags. The old bandage and gloves will be placed in the plastic Ziploc bag, the bag closed and then put in regular plastic trash bag for disposal.

#### **10.4 Compliance and Accountability**

Compliance and accountability will be monitored by the Investigational Chemotherapy

Service (ICS) according to their standards of practice (SOPs).

